4. STUDY OBJECTIVES

4.1 Overall Objective

The purpose of the present study is to evaluate whether the herbal drug Amara improves the subjective, perceived burden of abdominal symptoms in patients with functional dyspepsia. It will also assess if the treatment is well tolerated. The present study will also investigate psychological and physiological function. This additional information should provide insight into which patients benefit the most from the treatment with Amara. The results of this prospective, open-label therapeutic study will also inform the study design for any subsequent RCT study in functional dyspepsia.

4.2 **Primary Objective**

Document perceived changes in upper gastrointestinal, dyspeptic symptoms reported by patients with functional dyspepsia treated with Amara for 4 weeks, as assessed by the Leuven Dyspepsia Score between visit 1 (off treatment) and 3 (after treatment)..

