5. STUDY OUTCOMES

5.1 **Primary Outcome**

The primary outcome will be the perceived change of dyspeptic symptoms assessed by the Leuven Dyspepsia Questionnaire (LDQ) between visit 1 (off treatment) and 3 (after treatment). The questionnaire contains 3 domains/questions which related to: a) The inability to finish a meal due to early satiety b) The feeling of food lying heavily in the stomach c) Feeling bloated in the stomach. The questionnaire is presented to the patients in the form of three questions which define five grades of severity (0-4), and which are supported by pictograms expressing the associated severity. Higher total scores indicate more severe dyspeptic symptoms. For each subscale 0 normal, 1 mild dyspepsia; 2, moderate dyspepsia; 3, severe dyspepsia; 4, very severe dyspepsia. The questionnaire is to be evaluated on a daily basis and the mean of the values of the three symptoms is proposed to represent the severity of that day. A weekly score can be calculated from the daily scores and is currently proposed for the primary use of the scale.(21)

The LDQ has been developed using standard methods, including focus group interviews and cognitive debriefing interviews.(21) The further validation of the score was undertaken with the means of interventional studies, evaluating the response of this questionnaire to prokinetic and neuromodulatory medications. The LDQ has shown to be a good rating scale to be used as a severity indicator of dyspepsia and can be given to the same patient in subsequent sessions to track the change in symptoms. A minimally clinically important difference has also been determined. The results of this validation work have been published in peer reviewed journals.(22, 23)

The Leuven Postprandial Distress Scale, which is supported by the European Medicines Agency, is a sensitive and reliable patient-reported outcome instrument to assess symptoms in the functional dyspepsia/postprandial distress syndrome. Based on this information, the LDQ variable will be the main result to verify whether the test medication in this trial is efficacious. In this open-label study in which placebo and treatment effects are summed we expect a moderate to large >60% reduction in mean symptom burden as measured by the LDQ (results will be shown as mean \pm SD).

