At the end of the study, all participants will return the supply of Amara. The study team will assess compliance by counting the empty bottles and weighing partly used bottles. Patients will be asked whether they wish to continue the medication (yes / no). If the response is positive, then ongoing treatment will be recommended. Amara is classified by Swissmedic as dispensing category D available following discussion with specialist without prescription ("Abgabekategorie D: «Abgabe nach Fachgespräch»).

Overall, approximately 30 minutes will be needed to complete the questionnaires on each occasion. The total time required per patient during the study is a maximum of 8 hours (reading documents, filling in questionnaires, gastric emptying study (twice)).

During the period the participants are enrolled in this study no additional outpatient examinations are planned. If, while someone is participating in the study, acute symptom occur and the need arises for early outpatient assessment or inpatient admission to the clinic, the study would be terminated for this subject as of this date.

Limitations:

- The study will provide a prospective assessment of perceived treatment effectiveness; however, a large non-specific (placebo) effect is likely to be present as in any open-label, single-arm study in patients with functional gastrointestinal disease. This limitation is factored into the power calculation which requires at least a moderate treatment effect for Amara to be considered effective. Note that the secondary analysis that will identify baseline factors (e.g., age, sex, symptom severity, gastric emptying rate) that associate with treatment effect will be relatively less sensitive to this confounding factor.

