7.3 Assignment to study groups

The present trial is a single arm study.

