11.2 Determination of Sample Size

In this prospective open label study, placebo effects are likely to be present. Previous randomized controlled trials of therapy in functional gastrointestinal disorders indicate that this can be present in up to 40% of patients.(15) To compensate for this confounding factor and to demonstrate convincing

changes in perceived symptom burden at least 60% of patients should show improvement on-treatment compared to off-treatment (run-in phase). Assuming a moderate effect (Cohen's effect size of 0.4) on the primary outcome measure (effect size and standard deviation as in a previous paper by Carbone et al. (21)) power calculation suggests that 58 patients are required to detect a significant effect at a convincing level of statistical significance (beta 0.9, alpha <0.05). In the context of this study, the inclusion of 60 patients should also be sufficient to inform the design of any, future randomized, placebo-controlled study.

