11.4 Planned Analyses

The statistic evaluation will be performed with SPSS (IBM SPSS Statistics, NY: IBM Corp.), version 26 or higher or Graphpad Prism (MacKiev Software), version 9.3.1 or higher or higher for PC or Mac. The demographic data will be analysed with descriptive statistics as average ± standard deviation (SD) for continuous variables and with percentage of total (%) for categorical variables.

Differences between the scores from the primary and secondary endpoint variables – at baseline and after 4-weeks treatment - will be compared initially by t-test if the data is normally distributed and Wilcoxon rank sum test when data are not normally distributed. In addition, if data is normally distributed we will perform univariate and multivariate linear regression analysis in which potential covariates will be considered; confounding will be evaluated by adding these variables to the linear regression model and looking at the change of the regression coefficients. These variables will include participants age, gender, symptom severity, psychological state and gastric function (sensitivity, emptying) at baseline.

In the analysis of the primary outcome two-tailed $p \le 0.05$ will be considered statistically significant. Since the evaluation of the secondary endpoints is purely exploratory, other p-values will be calculated but reported without claiming significance,

Data will be transferred from the REDCap software to the statistics program Prism for evaluation, where data are password protected and only accessible to the persons involved in the study.

All analyses will be performed at Klinik Arlesheim by the research group of [name]. [name], Department of Gastroenterology, Klinik Arlesheim.

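### Section 6.1 says the baseline-factor analysis is less affected by placebo response, but a single arm cannot separate predictors of placebo response or recovery from predictors of benefit from Amara

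*Protocol*

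**What the plan says.** The study has one arm (section 7.3: "The present trial is a single arm study") and section 3.6 confirms that there is no comparator. In its limitations, section 6.1 accepts that "a large non-specific (placebo) effect is likely to be present as in any open-label, single-arm study". It then says that the secondary search for baseline factors linked to the treatment effect, naming age, sex, symptom severity and gastric emptying rate as examples, "will be relatively less sensitive to this confounding factor".

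The purpose is given in section 4.1: the additional measurements should give "insight into which patients benefit the most from the treatment with Amara". Section 4.3 lists the candidate predictors, severity of dyspeptic symptoms among them. Section 5.1 defines the primary outcome as LDQ change between visits 1 and 3. Sections 11.4.2 and 11.4.3 enter baseline LDQ as a covariate with age, gender, other gastrointestinal symptoms, psychological state, and gastric sensitivity and emptying. Section 11.4 plans univariate and multivariate linear regression and says that "confounding will be evaluated by adding these variables to the linear regression model and looking at the change of the regression coefficients".

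**The concern.** A slope of improvement on a baseline factor, estimated in treated patients only, is the sum of three parts: how the factor modifies the drug effect, how it modifies the placebo response, and how it relates to spontaneous change, including regression to the mean. Nothing in the data separates them. The search for predictors is therefore exposed to placebo response in much the same way as the mean change is, contrary to section 6.1.

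Severity has a further problem. Change is computed from the baseline score, so measurement error and day-to-day fluctuation in that score appear on both sides of the regression. The likely report is that patients with worse symptoms gain most, which the data would tend to show even if Amara did nothing. Sections 4.1 and 6.1 say the study's results are to inform a later randomised trial, so such a finding could influence who is enrolled or how that trial is stratified.

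**Working it through.** The protocol gives no figure for these regressions, so there is none to reproduce. Inputs from the protocol: 60 completers (section 7.4), LDQ change as outcome (5.1), baseline LDQ as covariate (11.4.2, 11.4.3), and entry requiring at least 2 of 4 on at least two subscales, total at least 4 (7.1). The test-retest correlation r of the LDQ is not given, so a range is assumed.

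**1. When would section 6.1 be right?** Slopes are unmoved by placebo response only if it is the same constant shift in every patient. Section 11.2 points the other way: trials "indicate that this can be present in up to 40% of patients", so some patients respond and others do not. As an illustration, let a factor act on the placebo response alone, at an assumed 0.3 SD per SD. In simulated trials of 60 (r = 0.5 and 0.7) it was nominally significant in 73% and 87% of models adjusted for baseline LDQ.

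**2. Baseline LDQ against improvement, no drug effect.** Let X be visit-1 and Y visit-3 LDQ, with equal variances s² and correlation r. Then Cov(X, X−Y) = s²(1−r) and Var(X−Y) = 2s²(1−r), so

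corr(X, X−Y) = (1−r)/√(2(1−r)) = √((1−r)/2).

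For example, r = 0.5 gives √0.25 = 0.50. Power by Fisher's z at n = 60 is Φ(atanh(corr)·√57 − 1.96). For r = 0.8: 0.327 × 7.55 − 1.96 = 0.51, which is 70%. Because every patient passes an entry cut, the last three columns repeat the test by simulation in a normal model, keeping only the upper part of the baseline distribution.

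| Assumed r | Correlation, no cut | Nominally significant, no cut | Upper 75% kept | Upper 50% kept | Upper 25% kept |
|---|---|---|---|---|---|
| 0.8 | 0.32 | 70% | 43% | 32% | 23% |
| 0.7 | 0.39 | 87% | 64% | 49% | 35% |
| 0.5 | 0.50 | 99% | 89% | 73% | 56% |
| 0.3 | 0.59 | over 99% | 97% | 90% | 76% |

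Simulations closer to the instrument (three integer 0–4 items, the section 7.1 entry rule, no treatment effect) gave correlations of roughly 0.14 to 0.36, nominally significant in about 15% to 84% of trials. The result depends on the item distribution and on the share of variance that is stable; a lower stable share gives a higher rate.

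**3. Other covariates.** Take a factor correlated 0.3 to 0.5 with the observed baseline LDQ and with no further link to the visit-3 score. With r of 0.5 to 0.7, it was nominally significant in 14% to 50% of univariate models of change. With baseline LDQ added, this fell to 4.3% to 5.3%. A factor that tracks stable severity rather than the score on the day can still be prognostic after adjustment, which is another reason not to call it a predictor of benefit.

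**4. The coefficient-change check.** Every patient is treated, so no model has a treatment coefficient. The nearest equivalent is time in a before–after model. Fixed baseline covariates take the same values at both times, so adding them leaves that coefficient unchanged (−0.4753 with and without them in a simulated data set of 60).

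**The case against.** Four points on the other side have force.

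- **The analyses are exploratory.** Section 11.4 reports secondary p-values without claiming significance, and section 6.1 itself says the design cannot evaluate efficacy. This lowers the stakes, and a rate of nominal significance counts for less where none is claimed. It does not make the sentence in 6.1 or the aim in 4.1 right; the disclaimer on efficacy sits badly with both.
- **The dependent variable is not named.** Sections 11.4 to 11.4.3 do not say whether the models take change or the visit-3 score. Change is inferred from sections 5.1 and 6.1. With baseline LDQ in the model, the other covariates have the same coefficients either way, so a baseline-adjusted visit-3 model may be what is meant.
- **Checking how coefficients move is ordinary practice among predictors.** A reader might infer from "confounding will be evaluated by adding these variables to the linear regression model" that the step is invalid, or that the trial will declare its treatment effect free of confounding. The protocol makes no such declaration, and comparing a factor's univariate and multivariate coefficients is legitimate. Only its use on the treatment effect is ruled out.
- **The problem is not uniform.** A reader might infer that false predictors are to be expected for every covariate, or that the severity artefact is almost certain. Neither is supported. The inflation concerns baseline LDQ and univariate models of factors correlated with it, and the 70% to over 99% figures ignore the entry cut that applies to every patient.

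**Conclusion.** The statement in section 6.1 is unsupported, and so is the aim in 4.1 of identifying who benefits most. A single arm can show who improves while taking Amara, but not who improves because of it.

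The coupling of baseline LDQ with change is real but conditional. It requires change as the dependent variable, and its size rests on assumed test-retest values: 0.32 to 0.59 without an entry cut, and roughly 0.14 to 0.36 with it, nominally significant in about 15% to 84% of trials of 60. The integer 0–12 total is also an assumption, since section 5.1 describes daily means and a weekly score as well. Other covariates stay near 5% each once baseline LDQ is in the model, provided that they do not modify placebo response and have no link to the visit-3 score beyond baseline LDQ.

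The primary before–after test does not depend on any of this. The correction could usefully be made and changes what may be concluded about predictors, but the trial does not stand or fall by it.

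**What to change.** - Delete the sentence in section 6.1 that calls the baseline-factor analysis less sensitive to the placebo effect.
- In sections 4.1, 4.3 and 11.4, describe the models as predictors of change during open-label use, not of benefit from Amara.
- In section 11.4, name visit-3 LDQ as the dependent variable and keep baseline LDQ in every model, including those that examine one further factor at a time. Do not interpret the baseline LDQ slope as a predictor of benefit.
- State in section 11.4 that the coefficient-change check concerns confounding among baseline predictors only and cannot assess confounding of the treatment effect.

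Two tempting additions should be left out. Centring the covariates does not turn the intercept of a visit-3 model into the mean change; it gives the mean visit-3 score. Replacing baseline LDQ by the run-in diary mean brings in a different artefact, because entry is selected on the screening LDQ. In simulations without a drug effect, the diary mean correlated with the fall at about −0.15 to −0.22 and was falsely significant in 20% to 40% of trials.

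The cost is wording and one model specification, with no new data. The price is a weaker claim about who benefits.

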6.2 Methods of minimising bias

6.2.1 Randomisation

Not applicable.

6.2.2 Blinding procedures

Not applicable.

6.2.3 Other methods of minimising bias

- Validated questionnaires will be used, and a statistical analysis plan is included in the protocol.
- Participants will record symptoms daily using a mobile application (paper version available). The study nurse will call participants if this technology is not used regularly.
- Objective assessment of gastric motor and sensory function will complement patient related outcome measurements.
- Compliance will be checked at the end of the treatment period.

6.3 Unblinding Procedures

Not applicable.

7. STUDY POPULATION

Patients with dyspeptic symptoms referred to gastroenterologists at Clinic Arlesheim for specialist investigation and management will be screened for eligibility.

7.1 Eligibility criteria

Participants fulfilling all of the following inclusion criteria are eligible for the study:

- Patients referred by their treating physician to the Center for integrative Gastroenterology at the Clinic Arlesheim
- Age over 18 years and \leq 75 years of age
- Patients with diagnostic criteria of Functional Dyspepsia with Postprandial Distress (Rome IV criteria) with Leuven Dyspepsia Score "at least moderate" severity (≥2/4) on at least two subscales (≥4 total). Normal endoscopy in previous 3 years.
- Signed informed consent
- No change in medical treatment (e.g., proton pump inhibitor, antidepressants) during the last one month or for the duration of the period
- No planned introduction or dose increases of (conventional) anxiolytics or antidepressants during the last one month or for the duration of the period
- Good German knowledge (at least level B2 from Common European Framework of Reference for Languages)

The presence of any one of the following exclusion criteria will lead to exclusion of the participant:

- Acute life-threatening conditions
- Withdrawal of informed consent
- Clinically relevant psychiatric comorbidity (HADS score >11 for anxiety or depression)
- Advanced liver (Child score > 6) or kidney disease (GFR < 60)
- History of major gastrointestinal surgery (appendectomy, hysterectomy, cholecystectomy, hernia repair are not exclusion criteria)
- Allergy to any component of Amara
- Treatment with Amara during the last one month prior to the study
- Pregnancy and lactation

7.2 Recruitment and screening

Patients referred for investigation of dyspeptic symptoms will be called by the department secretary or

a member of the team to make an appointment for their initial screening consultation at the Clinic Arlesheim. As also described in section 6.1, participants will then come to their initial consultation at the Clinic Arlesheim. If after this consultation the recruiting physician considers functional dyspepsia to be the diagnosis according to Rome IV classification, then the LDQ screening instrument will be used to confirm the presence and assess the severity of dyspepsia. A score of "at least moderate" severity (≥2/4) on at least two subscales (≥4 total) is the cut-off for study entry. Patients with clinically relevant, severe anxiety and depression will also be excluded (HADS ≥14). If no recent results are available, blood tests will be obtained to assess liver and kidney function. Total bilirubin, serum albumin, prothrombin time, ascites, hepatic encephalopathy and creatinine levels will be tested. At the screening visit, the LDS and HADS questionnaires will be completed at the time of recruitment and used as screening instruments. This data will be collected using an on-line application (paper versions also available). To rule out pregnancy, women of childbearing potential must take a pregnancy test.

If the patient fulfils all inclusion criteria and none of the exclusion criteria, the patient will be asked if she/he wants to participate. If she/he does want to participate, she/he will sign the informed consent form and will be included in the study. If desired, the study nurse will help the subjects to fill in the demographic details and further questionnaires detailed in the method above.

No payment will be given to study participants. Neither the subjects nor their health insurance companies incur additional costs in connection with participation in this study.

7.3 Assignment to study groups

The present trial is a single arm study.

7.4 Criteria for withdrawal / discontinuation of participants

In emergency situations, where acute symptoms develop or side effects are suspected to be associated with the Amara intake, treatment can be discontinued. The participation can also be terminated by the PI, by the Clinic Arlesheim or by the manufacturer of Amara if there is a suspicion of damage to health caused by the drug or a product defect, respectively. Also, as mentioned before, if there are any signs of patients unwilling to participate in the study it will result in the participant being excluded from the study.

If a participant does no longer fulfil the eligibility criteria at some point of the study, it will lead to the discontinuation of this participant from the study.

Participant recruitment will continue until 60 patients have completed the treatment arm of the study.

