An appointment will be made 2-4-weeks later for the second study visit at which time the ¹³C gastric emptying study will be performed again. The run-in period is 2-4-weeks. This reduces the influence of spontaneous "regression to the mean" (i.e., false positive results).(15)

Gastric motor and sensory function will be assessed by ingestion of the 400ml, 300kcal Nottingham Test Meal (NTM) labelled with ¹³C acetate. This provides both an assessment of patient symptoms / visceral sensitivity to gastric filling with the 400ml liquid nutrient meal and also an assessment of gastric emptying. The 400ml NTM can be ingested by >95% of patients with functional dyspepsia.(19,

24) The ¹³C isotope is not radioactive, it takes 2-hours to complete and this technique is very appropriate for repeated assessment of gastric emptying.(16) In a subset of 20 consecutive patients, gastric electrical activity will be measured before, during and after ingestion of the Nottingham Test Meal using the non-invasive Gastric Alimetry System (high-resolution gastric mapping / electro-gastrography). Concurrent heart rate monitoring will provide an assessment of cardiovagal tone / autonomic nervous function.

The treatment period with Amara drops is four weeks per patient; participants will be instructed to take 10-20 drops of the herbal medicine Amara three times a day before meals over 28 days. This treatment period is in accordance with previous studies for aromatic bitter substances and represents the minimum recommendation for study duration in functional gastrointestinal disorders.(15) During the treatment period patients will record their symptoms using a mobile application (reminder will be sent at 21:00 every day). In addition, patients can note side effects that they perceive to be caused by Amara. If participants do not regularly provide this information, then a team member will call to ask if they have any problems.

At the end of the treatment period the participant will return to Clinic Arlesheim for repeat assessment. The LDQ and other patient related outcomes will be assessed again and ¹³C gastric emptying study will be repeated on treatment.

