- In addition to subjective patient related outcome measures, repeat ¹³C breath testing with the Nottingham Test Meal on and off treatment will provide physiological assessment of effects of Amara on gastric motor and sensory function. Continuous assessment of patient sensations during Drink tests (i.e., gastric filling) may be less impacted by patient recall than questionnaires. ¹³C breath testing provides an indirect assessment gastric emptying based on the excretion of ¹³CO₂ in the expired air. Although well validated against scintigraphy, it remains uncertain to what extent these results can be affected by individual patient factors other than gastric emptying (e.g. metabolism). Note that this limitation will not affect the results of this study because we will compare gastric emptying in patients on and off Amara treatment (i.e., patients act as their own control).
- Amara drops will be distributed for self-administration at home, thus, we rely on participants to report their intake accurately. Compliance will be checked as described above.
- The four-week duration of drug intake is relatively brief and may underestimate the treatment effect.
- This study may suffer from the limitation that participants will take other over the counter medications or engage in other treatments at home.
- This study design does not allow evaluating the efficacy of Amara medication. However, the aim of this prospective study is to acquire results on overall effectiveness that will inform the design of a randomized controlled study with this aim.

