8.7 Concomitant Interventions (treatments)

Current medications, such as acid suppression or antidepressants, can continue to be taken by the participants during the study without dose increase or decrease. This also includes all self-purchased preparations that are available without a doctor's prescription and complementary-medical preparations. Participants will record the use of additional medication in the CRF. They also have to record if they are being treated by other physicians during the study.

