10.1.2 Reporting of serious adverse events (SAE) and other safety related events

As stated in the contract between the Clinic Arlesheim and Weleda AG, we will comply with our pharmacovigilance obligations. UAWs, SAEs and SUSARs will be reported to Weleda AG (see contact below) within a maximum of 24 hours. Any other side effects which are collected through the questionnaires will be notified to Weleda AG as soon as possible.

Address: WELEDA AG, [name]

Contact: [name], [contact], [contact]

Reporting of SAEs:

All SAEs must be reported immediately and within a maximum of $\underline{24 \text{ hours}}$ to the PI of the study. The PI will re-evaluate the SAE and make a causality assessment of the event to the study drug.

SAEs resulting in death are reported to the Ethics Committee via BASEC within 7 days.

If the possibility arises that a patient can admit the Clinic Arlesheim earlier than expected, it will lead to the discontinuation of this participant from the study. This hospital stay will not be considered as an SAE. Additionally, if a SAE is a clear result of the underlying disease, this SAE is exempted from expedited reporting.

Reporting of SUSARs

The Sponsor-Investigator needs to report SUSARs to the Ethics Committee via BASEC within 7 days, if the event is fatal, or within 15 days (all other events).

Reporting of Safety Signals

All suspected new risks and relevant new aspects of known adverse reactions that require safetyrelated measures, i.e. so called safety signals, must be reported to the Sponsor-Investigator within 24 hours. The Sponsor-Investigator must report the safety signals within 7 days to the Ethics Committee via BASEC.

Reporting and Handling of Pregnancies

Pregnant participants will be excluded from the clinical study

Periodic reporting of safety

An annual safety report is submitted once a year to the local Ethics Committee via PI.

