11.4.2 Primary Analysis

In the intention to treat analysis, all patients who have completed study questionnaires at baseline and after four-weeks of treatment will be included. Following covariates will be included in multivariate models: age, gender, dyspepsia symptom severity (LDQ), other gastrointestinal symptoms, psychological state and gastric function (sensitivity, emptying) at baseline.

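### The primary set labelled intention to treat holds only patients with both questionnaires; starters whose participation is ended early are not asked for a visit-3 LDQ and are replaced.

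*Protocol*

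**What the plan says.** **Primary set.** Section 11.4.2: "In the intention to treat analysis, all patients who have completed study questionnaires at baseline and after four-weeks of treatment will be included". Section 5.1 fixes the comparison as the LDQ at visit 1 against visit 3. Adherence plays no part in this set: under sections 8.4 and 11.4.3, taking less than half of the medication removes a patient only from the per-protocol analysis.

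**How participation ends.**
- Section 7.4: should a participant "no longer fulfil the eligibility criteria at some point of the study, it will lead to the discontinuation of this participant from the study". This ends study participation and not only treatment.
- Section 7.1 lists a criterion that runs on through the study: "No change in medical treatment (e.g., proton pump inhibitor, antidepressants) during the last one month or for the duration of the period".
- Section 6.1, on acute symptoms during the study: "need arises for early outpatient assessment or inpatient admission to the clinic, the study would be terminated for this subject as of this date".
- Section 10.1.2, where a patient can be admitted "earlier than expected, it will lead to the discontinuation of this participant from the study".

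**Text pointing the other way.** Section 8.7: "Participants will record the use of additional medication in the CRF". The limitations in section 6.1 foresee that "participants will take other over the counter medications or engage in other treatments at home". Section 7.4 makes stopping treatment for acute symptoms optional.

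**Data after an early end.** Section 9.2.5 waives follow-up for withdrawals due to exclusion criteria other than SAEs. For SAEs it lets assessments depend on the event. Section 8.5 keeps what was collected before withdrawal. That includes app entries, since "During the treatment period patients will record their symptoms using a mobile application".

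**Replacement.** Section 11.5 defines patients with only a screening or baseline questionnaire as dropouts and replaces them. Section 7.4 recruits until 60 have completed.

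**The concern.** An intention-to-treat set is meant to be fixed by what was known when treatment began. Here membership depends on answering a questionnaire four weeks later, and several rules stop some patients from reaching it. The triggers (acute symptoms, an unplanned assessment or admission, a change of other treatment) may well be related to how dyspepsia is going. In a single-arm study no control group undergoes the same selection, so nothing can offset it.

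Section 11.1 says the study exists to obtain an effect size for planning a confirmatory study. A reader who sees the intention-to-treat label will take the estimate as applying to everyone treated. It applies only to those who were still answering at the end, and the replacement rule restores the count of 60 without restoring the patients who left.

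**Working it through.** **1. Is the label right?** Section 11.4.2 requires both questionnaires. Section 11.5 calls a patient without the second one a dropout and replaces that patient. A starter with no visit-3 LDQ therefore cannot be in the set. It is an available-case set, kept regardless of adherence.

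**2. Is the missing LDQ collected anywhere else?**

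| Reason for early end | Section | Visit-3 LDQ requested? |
|---|---|---|
| Exclusion criterion other than an SAE | 9.2.5 | No, follow-up waived |
| SAE | 9.2.5 | Left open; none prescribed |
| Loss of eligibility in general | 7.4 | None prescribed |
| Early assessment or admission | 6.1, 10.1.2 | None prescribed |

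Section 9.3.2 ties the e-mailed questionnaire link to the third visit, which a patient whose study has ended no longer has. The daily app entries are kept under section 8.5, but they do not bring a patient into the set of section 11.4.2.

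**3. Which replacements matter?** Under section 9.3.2 Amara is provided at visit 2, after the run-in. Replacing patients lost before then is not selection after treatment, so only leavers who started Amara count below.

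**4. The plan's own figure.** Section 11.2 gives 58 patients for an effect of 0.4 with 90% power. The normal approximation for a paired comparison, two-sided 5%, is n = ((1.960 + 1.282)/0.4)² = 65.7, so 66; the exact t calculation gives 68. The 58 is not reproduced under the stated two-tailed test, but nothing in this point depends on it. Only the effect of 0.4 and the target of 60 completers are used.

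**5. Illustration.** The leaving rate f and the leavers' mean change L are assumptions; the protocol gives neither. The unit is the SD of the before-after change, and completers are set at 0.40.

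Starters needed for 60 completers = 60/(1 − f), rounded up:
- f = 10%: 60/0.9 = 66.7, so 67 starters, 7 leavers
- f = 20%: 60/0.8 = 75 starters, 15 leavers

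Mean in all starters if leavers do not change (L = 0):
- 60 × 0.40/67 = 0.358
- 60 × 0.40/75 = 0.320

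Share improved, taking the 60% expectation in section 11.2 (36 of 60) and counting leavers as not improved:
- 36/67 = 53.7%
- 36/75 = 48.0%

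The direction depends on L. Moving L the same distance to the other side of 0.40 (L = 0.80) gives 0.9 × 0.40 + 0.1 × 0.80 = 0.44 and 0.8 × 0.40 + 0.2 × 0.80 = 0.48. The completer figure is then too low. It is right only if leavers happen to change by the same 0.40.

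**The case against.** **The SAP may deal with missing data.** This stands for the imputation rule, which can be left there. It does not cover the rest. The protocol itself defines the set, its name, the replacement rule and the end of participation, and an SAP cannot analyse a visit-3 LDQ that was never requested.

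**Ending participation after a drug change is defensible in a single arm.** This also stands in part. Without a control group, an LDQ taken after a new drug credits that drug to Amara. The answer is to collect the value and mark it, because not collecting it leaves the selection unexamined.

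**The protocol is candid about its limits.** Section 6.1 accepts a large placebo effect and says efficacy cannot be evaluated. That lowers the stakes, but it does not make the set intention to treat.

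Several stronger readings are tempting and are not supported:
- *Only adherent patients are analysed.* Sections 8.4 and 11.4.3 keep poor adherers in the primary set. A patient who stops the drops but stays in the study can still give an LDQ.
- *Any added medication ends participation.* Section 8.7 and the limitations in section 6.1 suggest that some such patients stay. The text is unclear on which changes count.
- *Patients withdrawn for an SAE are barred from an LDQ.* Section 9.2.5 leaves this open.
- *The bias must flatter Amara.* Section 7.4 read literally would also remove patients who improve below the LDQ entry cut-off. That can hardly be intended, but it shows that the text does not fix the direction.

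**Conclusion.** The point holds and should be corrected before analysis. The set in section 11.4.2 consists of questionnaire completers and is mislabelled as intention to treat. Starters whose participation is ended are not asked for the visit-3 LDQ by any section, and they are replaced until 60 complete. The estimate is therefore selected by events after treatment began.

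Neither the size nor the direction of the bias can be taken from the protocol. With 10% to 20% leaving and no change in leavers, both assumed, 0.40 SD becomes 0.36 to 0.32 SD and 60% improved becomes 54% to 48%. With leavers who do better than completers, the error runs the other way.

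A reader might infer that a later trial would be mis-sized in the same proportion. That does not follow: the planned successor is placebo-controlled and would be sized on a between-group difference. No claim about power follows either, since that depends on how variable the leavers are and on the imputation rule. Replacement of run-in losses is not part of the problem.

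**What to change.** - **Sections 7.4 and 9.2.5:** separate stopping Amara from leaving the study. State that a medication change recorded under section 8.7 does not end data collection. Send the visit-3 LDQ by the existing e-mail link to every participant who started Amara and has not withdrawn consent.
- **Section 11.4.2:** define the intention-to-treat set as all who started Amara. Report the result in patients with both questionnaires beside it, under the name *completers*.
- **Section 11.5:** let replacement affect only the recruitment count. Keep replaced starters in the set, and report the number and reason of all early stops.
- **Other drugs:** flag LDQ values taken after a new or increased drug and show the result with and without them.

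Recruitment to 60 completers can stay, and the imputation rule for starters who never answer can go in the SAP.

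The cost is a few sentences in four sections, one extra questionnaire per discontinued patient and some added analysis. The estimate may turn out less favourable. Another drug's benefit may be credited to Amara: if, as an assumption, 10% of starters receive a drug worth 0.4 to 0.8 SD, the all-starter mean rises by 0.10 × 0.4 = 0.04 to 0.10 × 0.8 = 0.08 SD. The flagged analysis is there to expose this.
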